## 2. Study Procedures:

- a. **Initial Screening:** The initial screening will review inclusion/exclusion criteria by phone or online screener. Those eligible will be scheduled to complete an in-person visit within 14 days.
- b. **Final Screening (Day 0):** Participants will be instructed to smoke and vape as they normally would before the final screening. Final eligibility screening will be conducted in-person and will consist of a pregnancy test, exhaled carbon monoxide (eCO), providing evidence of EC use (bring EC to visit; dual users only), and obtaining informed consent. Participants will complete carbon monoxide (CO) measurement to confirm current smoking status (CO > 12 ppm). CO is collected by a simple, non-invasive breath test that involves the participant holding their breath for ~15 seconds and then exhaling into a straw connected to the CO monitor. Cigarette smoking will be assessed using the Timeline Followback (TLFB) in which individuals report on number of cigarettes per day (CPD) in the past 7 days. To assess baseline self-reported respiratory health, participants will complete the COPD assessment test (CAT). The modified Cigarette Evaluation Scale (mCES) will assess subjective effects and sensory experiences at the end of the session. Participant's intentions for future use (e.g., purchase, use) of ECs will be assessed using a 4-item measure. Participants will sample two e-liquid flavors (Menthol and Tobacco) to establish preference. Participants will go home with their device and e-liquid of choice to practice at home. Participants will complete baseline measures. Participants will be compensated \$10 for the final screening.
- c. **Human Lab Visit 1 (1-14 days after Final Screening):** At Human Lab Visit 1, participants will be re-screened according to inclusion/exclusion criteria. Pregnancy exclusion will be confirmed at each visit. They will be instructed to remain nicotine abstinent for 12 hours prior to the visit. Participants will complete CO measurement to confirm tobacco/nicotine abstinence. Participants will be provided with an overview of the study, and complete additional baseline self-report measures. Self-report will be used for EC abstinence, as there is currently no objective, reliable measure to verify non-use of these products within the time the participants will be in the lab. Cigarette smoking will be assessed using the TLFB in which individuals report on number of CPD in the past 7 days. Participants will be provided the device of their choice and pre-filled pod of their preferred e-liquid flavor. Participants will puff ad libitum for 30 minutes to establish baseline topography levels. Throughout the session, pre-intervention puff topography will be measured via a pressure sensor attached to the device/product and by the integrated topography software within the EC. This will not require anything additional of the participant. Blood sampling for changes in nicotine levels will occur at -5 minutes (pre-vaping session) and +30 minutes (immediately post-session). Self-reported levels of cigarette craving and withdrawal will be measured

using the Tiffany-Drobes Questionnaire on Smoking Urges – brief (QSU-brief) and Minnesota Nicotine Withdrawal Scale (MNWS) pre- and post-session. The mCES will assess subjective effects and sensory experiences at the end of each session. Participant's intentions for future use (e.g., purchase, use) of ECs will be assessed using a 4-item measure. At the end of the baseline vaping session, participants will be randomized and enrolled (stratified on EC history) to one of three study arms in a 1:1:1 fashion: 1) Brief Advice, 2) Single Episode Training, 3) Enhanced EC Training. See the Training Guild for Researcher for specific training. For the Brief Advice study arm, participants will be given brief advice to switch to the EC and basic instructions on use of the EC and refilling pods. Participants will view their topography post-intervention via the Escribe software while they puff. Based on our preliminary data, trained research staff will give feedback on puff parameters shown to differ between complete switchers and switch "failures" – puff duration, flow rate, inter-puff interval, and puff number. The session will last ~30 minutes. For the Enhanced EC training study arm, participants will receive the same training as the Single Episode Training arm. Participants will be asked to set a switch date using the Action Planning form. Participants will take the EC device home and use it as much or as little as they would like before the next visit. Lung function will be assessed via spirometry. At the end of the visit, a 6-minute walk distance (6MWD) test will be done to assess the participant's overall ability to conduct everyday activities. Baseline cardiovascular functioning will be measured using Pulse Wave Velocity, a sensitive measure of arterial stiffness that shows rapid (~1 month) changes with switching to ECs. Baseline beat-to-beat blood pressure will be measured to assess blood pressure and vascular elasticity. Participants will be compensated \$50 for this visit.

- d. **Human Lab Visit 2 / RCT Visit – Week 0 (1-5 days after Human Lab Visit 1):** Human Lab Visit 2 will occur 1-5 days after Human Lab Visit 2. Human Lab Visit 2 will be identical to Visit 1 but will not include any training, 6MWD test, or cardiovascular assessment. The purpose of this visit is to assess changes in topography following training at visit 1. Participants will be compensated \$50 for this visit.
- e. **Between Week 0 and Week 4:** Participants will be provided with the device of their choice and pre-filled pods to use between visits for the real-world switch period. If chosen, the Evolv Reflex EC device will collect and store 4 weeks of data on the participant's EC use patterns and puffing topography. The JUUL and Vuse devices do not collect data. Research staff will conduct a brief phone check in with all participants on their switch date. During this call, a trained research assistant will assess tobacco and nicotine use since the last visit and will briefly trouble shoot barriers to switching to the e-cigarette.
- f. **RCT Visit – Week 4:** At Week 4 topography data will be downloaded from the EC and reviewed. In addition, participants will return their used and unused pods which will be weighed to assess e-liquid consumption between visits. Those in the Brief Advice and Single Session Training arms will not receive additional training. For those in the Enhanced Training arm, they will receive additional real-time feedback on their puff patterns. This arm is intended to mimic the level of support provided to smokers making a quit attempt using traditional quit smoking strategies and to determine the minimum level of support necessary to achieve a pattern of predominant EC use. Our approach with this arm is intentionally flexible to match the needs of each participant over the course of behavior change. For the purposes of rapport-building and continuity of care, attempts will be made to have participants meet with the same staff member each session. For participants in all study arms, the following will be done. Topography will be used to objectively and passively measure EC puff patterns. Participants will again complete eCO measurement to confirm smoking status. Cigarette smoking will be assessed using the TLFB in which individuals report on number of CPD in the past 7 days. To

assess changes in self-reported respiratory health, participants will complete the CAT. Lung function will be assessed via spirometry. Self-reported levels of cigarette craving and withdrawal will be measured using the Tiffany-Drobes QSU-brief and MNWS. The mCES will assess subjective effects and sensory experiences at the end of each session. Participant's intentions for future use (e.g., purchase, use) of ECs will be assessed using a 4-item measure. At the end of the visit, participants will be provided another 4-week supply of pre-filled pods and encouraged to continue their switch. Participants will be compensated \$20 for this visit.

- g. **Between Week 4 and Week 8:** Participants will be provided with another 4-week supply of pre-filled pods to use between visits for the real-world switch period. The Evolv Reflex EC device will collect and store 4 weeks of data on the participant's use and puffing topography. The JUUL and Vuse devices do not collect data.
- h. **RCT Visit – Week 8:** Procedures at the Week 8 the visit will closely mirror Week 4 visit. Used and unused returned pods will be weighed. Topography data will be downloaded and reviewed. Those from the Enhanced EC Training study arm that have not achieved optimal topography or predominant EC use will receive real-time feedback on their puff patterns. Participants will again complete eCO measurement to confirm smoking status. Cigarette smoking will be assessed using the Timeline Followback (TLFB). To assess changes in self-reported respiratory health, participants will complete the CAT. Lung function will be assessed via spirometry. Self-reported levels of cigarette craving and withdrawal will be measured using the Tiffany-Drobes Questionnaire on Smoking Urges – brief (QSU-brief) and Minnesota Nicotine Withdrawal Scale (MNWS). The modified Cigarette Evaluation Scale (mCES) will assess subjective effects and sensory experiences at the end of each session. Participant's intentions for future use (e.g., purchase, use) of ECs will be assessed using a 4-item measure. Participants will be compensated \$20 for this visit.
- i. **Between Week 8 and Week 12:** Participants will again be provided with 4 weeks of pre-filled pods to use between visits for the real-world switch period. The Evolv Reflex EC device will collect and store 4 weeks of data on the participant's use and puffing topography. The JUUL and Vuse devices do not collect data.
- j. **RCT Visit – Week 12:** Participants will smoke and vape as they normally would. Participants will complete eCO measurement to confirm smoking status. Because the eCO is the only measure needed for this visit, visit location will be flexible. Visits will be conducted as determined by location and abilities of the study participant. Participants will be compensated \$10 for this visit.
- k. **Human Lab Visit 3:** Human Lab Visit 3 (Week 12) will be identical to Visit 1 (above) but will not include any training. The visit is intended to measure longer-term changes in EC puff patterns. Participants will be instructed to remain abstinent from nicotine and tobacco for 12 hours prior to the study visit. Participants will complete eCO measurement to confirm tobacco/nicotine abstinence. To assess changes in self-reported respiratory health, participants will complete the CAT. Lung function will be assessed via spirometry. Self-reported levels of cigarette craving and withdrawal will be measured using the Tiffany-Drobes QSU-brief and MNWS. The mCES will assess subjective effects and sensory experiences at the end of each session. Participant's intentions for future use (e.g., purchase, use) of ECs will be assessed using a 4-item measure. At the end of the visit, a 6-minute walk distance (6MWD) test will be done to assess the participant's overall ability to conduct everyday activities. Baseline cardiovascular functioning will be measured using Pulse Wave Velocity, a sensitive measure of arterial stiffness that shows rapid (~1 month) changes with switching to ECs. Baseline beat-to-beat blood pressure will be measured to assess blood pressure and vascular elasticity. Participants will be compensated \$50 for this visit.

- I. Monthly for 3 months post active study completion – phone follow up with participant.
3. Due to COVID-19 and the need to keep patients and researchers safe, we may use Zoom, a HIPAA compliant, university approved video conferencing software, during the visit. This will allow the participant to smoke freely (unmasked) while the researcher can watch and communicate with the participant via video conferencing from outside the clinic room. We will only enter the room when necessary and will ensure the participant is masked when research staff are present.
4. All procedures, tests, and visits are being performed solely for research purposes and are not billable to insurance.
5. Samples will be labeled with a unique participant and study identification numbers, participant initials, visit date, and timepoint (-5, +30) and only members of [name] and [name]'s teams will have access to the samples. Samples will be disposed of one month after the final report is sent out to the Principal Investigator.
6. Timeline: We anticipate that this study will last 1 year (12 months; See Table 2 for timeline). We expect to recruit 5 participants in the third month of Q1 and 18 participants in each Q2 and Q3 and 4 participants in the final quarter. This accrual rate is commensurate with our past studies.

Table 2. Study timeline by quarter

Quarters (3 months)	Q1	Q2	Q3	Q4	Post-award
Staff training, REDCap, IRB	X				
Participant recruitment (N = 45)	5	18	18	4	
Human Lab Visits	X	X	X	X	
RCT	X	X	X	X	
Processing/sample analysis				X	
Data analysis				X	X
R01 preparation			X	X	X
Dissemination			X	X	

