**Smokers:**

Use of tobacco products other than cigarettes including e-cigarettes in the past 30 days, current use of cessation medications, pregnant, planning to become pregnant, or breastfeeding, recent history of cardiovascular or pulmonary events in the past 3 months, household member current or previously enrolled in the study, weekly use of an EC over the last 6 months

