**Dual Users:**

Use of tobacco products other than cigarettes and e-cigarettes in the past 30 days, current use of cessation medications, pregnant, planning to become pregnant, or breastfeeding, recent history of cardiovascular or pulmonary events in the past 3 months, household member current or previously enrolled in the study

3. Withdrawal/Termination criteria:

Participants will be instructed to present to the lab nicotine deprived (12 hours abstinent) for the first study visit. If participants present to the first study visit with an eCO  $>12$  ppm or they report other nicotine use on two separate study visits, they will be withdrawn from the study (i.e., participants will be rescheduled one time).

4. Participants will not be allowed to participate in another research study that aims to alter their tobacco use during this research study.

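### EC-naive smokers use study e-cigarettes from Day 0, then are re-screened at Visit 1 under an exclusion for any e-cigarette use in the past 30 days, with no exemption for study product

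*Protocol*

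**What the plan says.** Four parts of the Protocol bear on this.

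- **II.D.2, Exclusion criteria, Smokers** (the EC-naive group) lists "Use of tobacco products other than cigarettes including e-cigarettes in the past 30 days". It separately lists "weekly use of an EC over the last 6 months".
- **II.D.2, Exclusion criteria, Dual Users** has the parallel item "Use of tobacco products other than cigarettes and e-cigarettes in the past 30 days", so ECs are a permitted product for that group only.
- **II.E.2.b, Final Screening (Day 0)** gives all participants EC exposure: "Participants will sample two e-liquid flavors (Menthol and Tobacco) to establish preference", after which "Participants will go home with their device and e-liquid of choice to practice at home". Neither step is limited to one group, although the same paragraph does limit the bring-your-EC check to dual users.
- **II.E.2.c, Human Lab Visit 1** takes place 1-14 days after Final Screening and opens with this step: "At Human Lab Visit 1, participants will be re-screened according to inclusion/exclusion criteria". Randomisation and enrolment, stratified on EC history, come at the end of that visit's baseline vaping session.

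No section exempts study-supplied EC use, ties the 30 days to the period before Final Screening, or limits which criteria are checked again.

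**The concern.** The trial gives naive participants an EC and then checks them against a rule that forbids recent EC use. The second check comes before randomisation, so as written it decides who can enter.

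II.B and II.C.1 name EC history (naive versus current use) as the stratification factor. If the rule is enforced as worded, the naive stratum cannot be filled. If it is not, each staff member has to decide what counts as EC use and from what date. Eligibility may then differ between participants in the same position, and enrolled naive participants carry an apparent eligibility deviation. The protocol also gives no date at which naive status is determined, although by randomisation every naive participant has used an EC on the study's instruction.

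**Working it through.** The plan states no figure for this point. The check is one of dates and wording.

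**Inputs**
- Look-back for the naive group: 30 days (II.D.2, Smokers).
- First study EC exposure: Day 0, flavour sampling (II.E.2.b).
- Further exposure: home practice from Day 0 until Visit 1 (II.E.2.b).
- Visit 1: day d after Final Screening, with d from 1 to 14 (II.E.2.c).

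**Step 1: does the look-back reach Day 0?** At Visit 1 the look-back runs from day d − 30 to day d.

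| Visit 1 on day | Look-back starts | Look-back ends | Contains Day 0? |
|---|---|---|---|
| 1 | 1 − 30 = −29 | 1 | yes |
| 14 | 14 − 30 = −16 | 14 | yes |

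Day 0 drops out only when d − 30 > 0, that is from day 31. The latest permitted visit is day 14. Day 0 and the whole practice period therefore lie inside the window at every permitted visit date.

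**Step 2: is home practice needed to trigger the exclusion?** No. Sampling at Day 0 is already EC use. A naive participant who never opened the device at home still meets the 30-day item at Visit 1.

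**Step 3: does the other EC item matter?** The six-month weekly-use item would not be met by 1-14 days of practice. The conflict comes from the 30-day item alone.

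**Step 4: could such a participant pass as a dual user instead?** No. II.D.1 requires dual users to have used an EC on more than 15 of the last 30 days, for the past 3 months. Day 0 to day 14 inclusive is at most 15 days, and the 3-month condition fails as well. Read literally, the participant fits neither group.

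**Step 5: could the naive-group wording be read as allowing ECs?** The phrase is loose, but the dual-user item names ECs as a permitted product and the naive item does not. Together with the naive label, that contrast supports reading it as an exclusion. Nor can the device taken home be a naive participant's own EC; it has to be study-supplied.

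**Step 6: where does the re-screen fall relative to allocation?** The order at Visit 1 is re-screen, baseline vaping session, randomisation. The conflict affects who enters, before an arm is assigned.

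**The case against.** The strongest reply is that the protocol already points to Day 0. II.E.2.b calls that visit the final eligibility screening and checks dual users' ECs there. III.B says eligibility is verified by phone and at the initial in-person visit, which it describes as final enrolment. The groups are thus separated before any study e-liquid is sampled, and a reading that empties a stratum the trial plainly means to enrol is unlikely to be the one intended or applied.

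This stands as evidence of intent, and it makes actual loss of the stratum unlikely. It does not remove the contradiction. II.E.2.c expressly applies the criteria again at Visit 1 and places enrolment there, which also disagrees with III.B on when eligibility is settled.

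Three stronger readings are tempting, and the documents do not support them.

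- *The rule removes those who practise and keeps those who do not.* This does not follow. Day 0 sampling catches both, so the literal rule does not select on home practice.
- *Case-by-case decisions in an open-label trial bias the comparison of arms.* The re-screen precedes allocation. Arm-dependent decisions would require staff to know the next assignment at that moment, and nothing in the protocol says they do.
- *EC history is the only stratification factor.* II.B, II.C.1 and II.E.2.c name no other, but V.A mentions gender among the stratification variables. The point needs only that EC history is the factor named for randomisation.

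**Conclusion.** The contradiction is real, and the text is wrong as written. On a literal reading all naive participants become ineligible at Visit 1, at every permitted visit date. That describes what the wording does; it is not a forecast of losses, since staff would almost certainly disregard the wording. The protocol gives no planned split of the 45 participants by EC history, so the number affected cannot be stated.

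The practical consequence is inconsistent eligibility decisions and avoidable deviations. No bias in the between-arm contrast in puff duration has been shown.

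The conclusion rests on two assumptions: that the Visit 1 re-screen covers all criteria, since the text names no subset, and that sampling a flavour means vaping it. If sampling did not involve vaping, home practice would be the trigger instead, and the contradiction would remain for anyone who practised as directed.

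**What to change.** Reconcile the three places with one sentence in each of two sections.

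- **II.D.2 (Smokers):** the 30-day EC-use exclusion, and the EC-history stratum used at randomisation, are determined as of Final Screening (Day 0), before any study product is used.
- **II.E.2.c:** EC use supplied by the study since Final Screening does not count against that exclusion when criteria are checked again at Visit 1.

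II.E.2.b can stay as it is. It would help to align III.B with II.E.2.c on when enrolment occurs.

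The cost is a short text amendment. Sample size, visits, assessments and analysis do not change. If participants have already been re-screened, the sponsor should record which reference date was used for each.

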**Aim 1:** Understand differences in acute (i.e., in-lab) changes in puff patterns (i.e., puff duration), cigarette craving, and nicotine exposure from pre- to post-EC training/brief advice between smokers who received brief advice versus EC training (single episode and enhanced EC training arms combined). Smokers who receive EC training will show greater increases in puff duration compared to brief advice (*H1a*), greater reductions in cigarette craving compared to brief advice (*H1b*), and greater increases in nicotine exposure compared to brief advice (*H1c*).

**Aim 2:** Determine the longer-term impact of EC training and training dose on switch patterns (i.e., % predominant EC users), health effects (i.e., changes in cardiovascular health, functional activity, lung function) and puff patterns. In a dose response pattern, enhanced EC training will result in the greatest proportion of predominant EC users at Wk12 (*H2a*), the greatest improvements in health outcomes at Wk12 (*H2b*), and the greatest increases in puff duration from baseline to Wk12 (*H2c*) followed by single session training and brief advice.

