### C. Sample size, statistical methods, and power calculation

1. 45 eligible smokers with COPD will be stratified by EC use history (naïve vs. current use) and randomized (1:1:1) to receive brief advice to switch to ECs, single session EC training, or enhanced EC training. Randomization will be determined by computer-generated random numbers. After baseline data collection has been completed, the research assistant will select the sequential study ID number to determine the randomization assignment.
2. This is an open-label trial. There is no blinding involved.
3. Based upon preliminary data, the standard of change in puff duration over two weeks was 1.5 seconds per puff. Assuming a common standard deviation across groups, 15 participants will allow us to obtain a 95% CI with a margin of error of 0.76 for the mean change for brief advice. In the acute phase (i.e., human lab visits 1 and 2), the single episode and enhanced EC training arms will have the same amount of intervention and will be combined. Thus, 30 participants will allow us to obtain a 95% CI with a margin of error of 0.54 for the mean change in puff duration in the combined intervention groups. We also wish to estimate the proportion of subjects who are predominant or complete switchers at Week 12. Fifteen participants in each group will allow us to estimate the 95% CI for the proportion of switchers in each group with a margin of error no greater than 0.25. This data will allow us to determine the sample size needed for a fully powered randomized trial. For the purposes of the current study, we will need 15 complete cases for each group. Due to potential attrition, we will recruit up to 22 participants per group. We will discontinue recruitment when we have 15 complete cases per group.

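### The baseline 6-minute walk, and possibly the other H2b health measures, is taken after randomisation and training at Human Lab Visit 1, against the protocol's own randomisation rule

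*Protocol*

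**What the plan says.** Section II.E.2.c sets out Human Lab Visit 1. On abstinence it says: "They will be instructed to remain nicotine abstinent for 12 hours prior to the visit". The vaping session comes next: "Participants will puff ad libitum for 30 minutes to establish baseline topography levels". Then: "At the end of the baseline vaping session, participants will be randomized and enrolled (stratified on EC history) to one of three study arms". The arm's advice or training follows, with a session of about 30 minutes, and then the health tests: "Lung function will be assessed via spirometry. At the end of the visit, a 6-minute walk distance (6MWD) test will be done". Baseline pulse wave velocity and beat-to-beat blood pressure are described last, with no time attached.

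Section II.C item 1 gives a different sequence: "After baseline data collection has been completed, the research assistant will select the sequential study ID number to determine the randomization assignment". Section II.B places training at the end of Visit 1, which is also where II.E.2.c places the 6MWD.

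Section II.E.2.d removes the 6MWD and the cardiovascular assessment from Visit 2 (Week 0). Section II.E.2.k says that Visit 3 "will be identical to Visit 1 (above) but will not include any training", and again puts the 6MWD last. Section V.A analyses the health effects as change to Week 12, with confidence intervals on the differences in change between arms. Section II.C item 2 states that there is no blinding.

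**The concern.** A baseline should be unaffected by the allocation it is later used to compare. Here the 6MWD baseline is collected after the arm is known to participant and staff and, in the order described, after the arm's intervention has been given. The walk depends on effort, so knowledge of the arm can enter it. If training involves extra puffing, acute exposure just before the test can also differ by arm.

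H2b is meant to show the longer-term effect of training on cardiovascular health, functional activity and lung function. Section V.A says the pilot exists to supply effect sizes for a fully powered trial. A distortion of the baseline would pass into those effect sizes. No later analysis can remove it, because for 6MWD and the cardiovascular measures no other baseline is scheduled.

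**Working it through.** **1. Order of events, measure by measure.** Three events matter at Visit 1: the end of vaping, randomisation and the intervention.

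| Measure | Time stated in II.E.2.c | Position in the text | Under II.C item 1 |
|---|---|---|---|
| 6MWD | Yes, end of visit | After training | Before randomisation |
| Spirometry | None | After training | Before randomisation |
| Pulse wave velocity | None | After training | Before randomisation |
| Beat-to-beat blood pressure | None | After training | Before randomisation |

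For 6MWD the conflict cannot be read away. Randomisation is tied to the end of the vaping session, and a test that closes the visit comes later. This holds even if II.B is followed and training competes with the walk for the last place: the walk is still after allocation. For the other three, sentence order suggests the same, but the section is not strictly chronological. For example, it describes taking the device home before it describes spirometry. Section II.G adds that cardiovascular testing takes place in a separate laboratory, without saying when in the visit.

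**2. What enters the H2b contrast.** For arm a, let C be the longer-term effect, and let A1 and A3 be the acute shifts at Visits 1 and 3.

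- Observed change in arm a = C(a) + A3(a) − A1(a).
- Difference between training (T) and brief advice (B) = [C(T) − C(B)] + [A3(T) − A3(B)] − [A1(T) − A1(B)].

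An acute effect that is the same in both arms cancels. A1 has two parts. The 30-minute vaping session precedes randomisation, so its arm difference is zero in expectation. The intervention session comes after it and can differ by arm. A3 has no training component; it differs only if training has changed how people puff by Week 12. The net bias is the arm difference in A3 minus the arm difference in A1. A shift in the 6MWD baseline from knowledge of allocation acts in the same way as A1.

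**3. Size.** The protocol gives no precision figure for any H2b outcome and no acute effect on any of them, so the bias cannot be computed. The margins it does give, for other outcomes, follow from the normal approximation:

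- 1.96 × 1.5/√15 = 0.759 (stated 0.76)
- 1.96 × 1.5/√30 = 0.537 (stated 0.54)
- 1.96 × √(0.25/15) = 0.253 (stated as no greater than 0.25)

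On the same basis, with 15 per arm and a common SD of change, the standard error of a difference in change is SD × √(2/15) = 0.365 SD, and the 95% half-width is 1.96 × 0.365 = 0.72 SD. With a net bias of b SD, coverage is Φ(1.96 − b/0.365) − Φ(−1.96 − b/0.365).

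| Assumed net bias (SD of change) | Coverage of nominal 95% CI |
|---|---|
| 0.1 | 94.1% |
| 0.2 | 91.5% |
| 0.3 | 87.0% |
| 0.5 | 72.2% |

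The values of b are assumptions chosen to show the range; none comes from the protocol.

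**The case against.** The strongest reply is that this is mainly loose drafting. Three of the four measures have no stated time, and II.C item 1, taken literally, puts them before randomisation. The pre-training vaping is balanced in expectation. H2b is a secondary aim in a 45-person pilot, and against a half-width of 0.72 SD a small bias does little to coverage. All of that stands. It does not rescue the 6MWD, whose time is explicit, and it leaves the order of the other three for staff to decide.

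A reader might go further and infer that all the H2b changes are contaminated by acute nicotine effects that differ by arm. The documents do not support that:

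- Post-training measurement is stated only for 6MWD.
- A figure of 60 against 30 minutes of device exposure would count the whole training session as puffing. No amount of puffing is given, and the sentence about puffing while viewing topography has no arm label. Its context does point to the training arms, since feedback on puffing is what separates them from brief advice.
- The remark in II.E.1 on sensitivity to smoking and vaping concerns changes in use status, not the response to a single session.
- H1c predicts "greater increases in nicotine exposure compared to brief advice", but for the acute phase. H2c concerns puff duration. Unequal nicotine intake at Week 12 is an extrapolation from these.
- The two acute terms enter with opposite signs and may partly offset, so no direction can be claimed.

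There is also a fair objection to moving the tests. Visit 2 has no 6MWD, so walking before vaping at Visit 1 only could alter puffing between the two visits that define the primary endpoint. Any such effect would precede randomisation and be common to all arms, so it would not bias the between-arm contrast. It could affect the within-arm changes, which is why a rest is needed.

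**Conclusion.** The point holds for 6MWD as written: its only baseline is taken after randomisation in an open-label trial, contrary to II.C item 1. For pulse wave velocity, beat-to-beat blood pressure and spirometry, the protocol leaves a contradictory order that permits the same fault. At Week 12 the 6MWD again comes at the end of a visit with a vaping session.

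The between-arm difference in change can therefore include knowledge of allocation at baseline and arm differences in acute exposure. The latter depends on puffing during training at Visit 1 and on whether training has changed puffing by Week 12. Sign and size cannot be determined from the documents; the coverage figures rest on assumed biases, a common SD and 15 complete cases per arm. This should be fixed, but it affects a secondary aim and leaves the between-arm contrast on the primary endpoint, change in puff duration, intact.

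**What to change.** Amend II.B, II.C item 1, II.E.2.c and II.E.2.k so that they give one sequence. At Visit 1, complete spirometry, pulse wave velocity, beat-to-beat blood pressure and 6MWD before randomisation and training, preferably after the abstinence check and before the vaping session. At Visit 3, keep the same order of tests relative to vaping.

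No new test or visit is needed, and the 12-hour abstinence already provides the window. There are two costs. The cardiovascular laboratory slot must come earlier in both visits, and a rest must be scheduled between the 6MWD and vaping to protect the comparison of puffing at Visits 1 and 2. If that comparison is the overriding worry, moving only randomisation and training to after the tests would remove the conflict with II.C item 1 and the post-allocation baseline. The tests would then still follow vaping, and any Week 12 difference in acute exposure would remain. The change has to be in place before participants reach Visit 1, since a baseline already taken after allocation cannot be recovered.
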